## 9.2.5. Exclusion criteria

Patients meeting any of the following criteria will not be included in the study:

- ≥1 prescription dispensing of tofacitinib in the selected databases in the 12 months *prior to* the indexing period; and/or
- Patients with an index tofacitinib prescription dispensing for an indication for which the original aRMM materials for that indication were not yet distributedc.

For example, if a patient indexes with a tofacitinib prescription dispensing for UC in Sweden prior to September 2018 (the date of full distribution of the original aRMM materials), they will be excluded from the study. For a patient that has another (unapproved) or unknown indication, the date of the earliest original aRMM materials distribution for an indication, specific to the patient's country (i.e., May 2017 in Sweden, December 2018 in Hungary, May 2017 in the Netherlands, and April 2017 in Germany), will be used to evaluate this criterion.

## 9.3. Variables

### 9.3.1. Outcomes

The primary outcomes of interest will be (see Table 3 for operational definitions):

- The demographics, comorbidities, and prior and current medications (including prior use of biologics) of tofacitinib patients;d,e
- Prescribers' adherence to the tofacitinib aRMMs, specifically:
  - Compliance to the recommended posology per indication and duration of use, as measured by:f
    - ADD of tofacitinib therapy, calculated in 8-week intervals from Week 0 through Week 47, and reported in the following categories:
      - Up to 5 mg ADD;
      - >5 to 11 mg ADD;

<sup>c This exclusion criterion will primarily apply to those patients who received their index tofacitinib prescription for an indication within the first 3 months after approval of that indication.

<sup>d The data sources are unable to reliably ascertain severity of hepatic impairment and renal impairment.

<sup>e In GKV claims, outpatient diagnoses are reported quarterly.

<sup>f The study outcomes that contain an ADD component will *not* be assessed in Hungary or the Netherlands. The Hungarian administrative claims database is unable to estimate ADD, either directly or by proxy, due to how tofacitinib is captured in the database. In the high-budget impact medication dataset of the PHARMO Database Network (Netherlands), neither ADD nor the number of pills per prescription is captured.

- >11 to 15 mg ADD;
- >15 to 20 mg ADD; and
- >20 mg ADD;

Note that within these reporting intervals and categories, ADD will also be reported by approved indication or by the indication groups: "PsA or RA" and "UC", presence of  $\geq$ 1 VTE risk factor prior to tofacitinib initiation, and prior use of an alternative therapy (i.e., biologic) in the 12 months prior to tofacitinib initiation; depending on the objective, outcomes will be stratified by reporting period;e,g

- The proportion of patients with an ADD of >11 mg during any of the 8-week follow-up intervals and no evidence of a diagnosis for UC; and
- The proportion of patients with an ADD of ≥15 mg in Weeks 16-23, Weeks 24-31, Weeks 32-39, and/or Weeks 40-47 of follow-up with evidence of a diagnosis for UC but no use of an alternative therapy (i.e., biologic) *prior to* tofacitinib initiation;
- Compliance to patient screening and laboratory monitoring prior to and during tofacitinib treatment, as measured by:h
  - The proportion of patients with evidence of having received the following recommended screenings *prior to* initiation of tofacitinib:
    - Creatinine (serum or urine) laboratory testing;
    - TB screening;
    - Viral hepatitis B and C screening;
    - ALC laboratory testing;
    - ANC laboratory testing;
    - Haemoglobin laboratory testing; and

<sup>g Hungary will not have a VTE Reporting Period 1. Hungary will also not have a VTE Reporting Period 2 for PsA and UC.

<sup>h This outcome (and all sub-outcomes) will *not* be assessed in Sweden because the Swedish national health registers do not capture the laboratory tests of interest. In GKV claims, it may not be possible to differentiate an ALC laboratory test from an ANC laboratory test, or an ALT laboratory test from an AST laboratory test. In the PHARMO Database Network, TB screening and viral hepatitis B and C testing are not captured.

- ALT and/or AST laboratory testing (i.e., liver function testing);
- For patients with 6 and 12 months of tofacitinib therapy, the proportion of patients with evidence of having received the following recommended monitoring *after* initiation of tofacitinib in the respective periods:
  - TB screening;
  - Viral hepatitis B and C screening;
  - ALC laboratory testing;
  - ANC laboratory testing;
  - Haemoglobin laboratory testing;
  - ALT and/or AST laboratory testing; and
  - Lipid panel (i.e., total cholesterol, high-density lipoprotein [HDL], lowdensity lipoprotein [LDL], and triglycerides [TG]) laboratory testing;
- Compliance to recommendations to limitations for use, including
  - Use in patients with VTE risk factors, as measured by:e
    - The proportion of patients with evidence of  $\geq 1$  VTE risk factors *prior to* initiation of tofacitinib, reported overall and by approved indication;
    - The number of VTE risk factors identified *prior to* initiation of tofacitinib, reported overall and by approved indication;
    - The proportion of patients with UC who have: ≥1 VTE risk factor identified *prior to* tofacitinib initiation; no use of an alternative therapy (i.e., biologic) *prior to* tofacitinib initiation; and an ADD >10 mg in Weeks 16-23, Weeks 24-31, Weeks 32-39; and Weeks 40-47 of follow-up;f
    - The proportion of patients who discontinue to facitinib after developing  $\geq 1$  VTE risk factor while taking to facitinib; and
    - The proportion of patients who continue taking tofacitinib after developing  $\geq 1$  VTE risk factor while taking tofacitinib;
  - Use in patients aged 65 years and older, as measured by:
    - The proportion of patients 65 years and older with no alternative treatments *prior to* initiation of tofacitinib, reported overall and by approved indication;

- The proportion of patients aged 65 years, receiving tofacitinib, who have 0 prescription dispensings of tofacitinib from the time they turn 65.5 years old through to the end of the follow-up period, reported overall and by approved indication;
- The proportion of patients aged 65 years, receiving tofacitinib, who have ≥1 prescription dispensing of tofacitinib from the time they turn 65.5 years old through to the end of the follow-up period and no history of alternative treatments *prior to* that tofacitinib prescription dispensing, reported overall and by approved indication; and
- The proportion of patients aged 65 years, receiving tofacitinib, who have ≥1 prescription dispensing of tofacitinib from the time they turn 65.5 years old through to the end of the follow-up period and a history of alternative treatments *prior to* that tofacitinib prescription dispensing, reported overall and by approved indication;
- Use in patients with CV risk factors, as measured by:e
  - The proportion of patients with evidence of  $\geq 1$  CV risk factors *prior to* initiation of tofacitinib, reported overall and by approved indication;
  - The proportion of patients with evidence of ≥1 CV risk factors *prior to* initiation of tofacitinib and no prior use of an alternative therapy (i.e., biologic), reported overall and by approved indication;
  - The proportion of patients who discontinue to facitinib after developing  $\geq 1$  CV risk factor while taking to facitinib; and
  - The proportion of patients who continue taking tofacitinib after developing ≥1 CV risk factor while taking tofacitinib;
- Use in patients with malignancy risk factors, as measured by:e
  - The proportion of patients with evidence of  $\geq 1$  malignancy risk factors *prior to* initiation of tofacitinib, reported overall and by approved indication;
  - The proportion of patients with evidence of ≥1 malignancy risk factors *prior to* initiation of tofacitinib and no prior use of an alternative therapy (i.e., biologic), reported overall and by approved indication;
  - The proportion of patients who discontinue tofacitinib after developing ≥1 malignancy risk factor while taking tofacitinib; and
  - The proportion of patients who continue taking tofacitinib after developing ≥1 malignancy risk factor while taking tofacitinib;

- Contraindicated use, as measured by:e
  - A patient *initiating* tofacitinib therapy if they have severe hepatic impairment;i
  - A woman *initiating* tofacitinib therapy if she is pregnant;
  - A patient *initiating* tofacitinib therapy if they have or have had TB in the prior 2 months;
  - A patient initiating tofacitinib therapy if they have or have had a serious and/or opportunistic infection in the prior 2 months; and
  - A woman *receiving* tofacitinib therapy during her pregnancy;
- Use with concomitant medications not compatible with tofacitinib, as measured by:
  - The proportion of patients receiving biologics and/or potent immunosuppressants *while taking* tofacitinib; and
  - The proportion of patients receiving a live vaccination *while taking* tofacitinib;j

The secondary outcomes of interest will be:

- Tofacitinib prescribing patterns over time;e,f and
- Changes in the prescribing patterns (utilisation) of tofacitinib following the updated recommendations and limitations for use implemented after the 2019 Article 20 referral and the 2021 signal evaluation procedure, specifically:
  - Use in patients with VTE risk factors, as measured by:e,f
    - The proportion of patients with evidence of ≥1 VTE risk factors *prior to* initiation of tofacitinib, reported overall and by approved indication and stratified by VTE Reporting Periodk

<sup>i The data sources are unable to reliably ascertain severity of hepatic impairment; thus, this sub-outcome may be overestimated.

<sup>j This sub-outcome will not be assessed in Sweden because most vaccinations are not done in specialist care and therefore are not captured in the National Patient Register (NPR), nor are vaccines prescribed and purchased by the patients in the pharmacies and therefore are not be captured in the Prescribed Drug Register (PDR). Vaccination data are also unavailable in the PHARMO Database Network. In GKV claims, it is not possible to differentiate between live and non-live vaccines.

<sup>k Hungary will not have a VTE Reporting Period 1. Hungary will also not have a VTE Reporting Period 2 for PsA and UC.

- The number of VTE risk factors identified *prior to* initiation of tofacitinib, reported overall and by approved indication and stratified by VTE Reporting Periodk
- The proportion of patients with UC who have: ≥1 VTE risk factor identified *prior* to tofacitinib initiation; no use of an alternative therapy (i.e., biologic) *prior to* tofacitinib initiation; and an ADD >10 mg in Weeks 16-23, Weeks 24-31, Weeks 32-39; and Weeks 40-47 of follow-up, stratified by VTE Reporting Periodf,k
- The proportion of patients who discontinue tofacitinib after developing ≥1 VTE risk factor while taking tofacitinib, reported overall and by approved indication and stratified by VTE Reporting Periodk
- The proportion of patients who continue taking tofacitinib after developing ≥1 VTE risk factor while taking tofacitinib, reported overall and by approved indication and stratified by VTE Reporting Periodk
- Use in the elderly (patients 65 years and older), as measured by:
  - The proportion of patients 65 years and older with no alternative treatments *prior to* initiation of tofacitinib, reported overall and by approved indication and stratified by VTE Reporting Periodk and CV and Malignancy Reporting Periodl
  - The proportion of patients aged 65 years, receiving tofacitinib, who have 0 prescription dispensings of tofacitinib from the time they turn 65.5 years old through to the end of the follow-up period, reported overall and by approved indication and stratified by VTE Reporting Periodk and CV and Malignancy Reporting Periodl
  - The proportion of patients aged 65 years, receiving tofacitinib, who have ≥1 prescription dispensing of tofacitinib from the time they turn 65.5 years old through to the end of the follow-up period and no history of alternative treatments *prior to* that tofacitinib prescription dispensing, reported overall and by approved indication and stratified by VTE Reporting Periodk and CV and Malignancy Reporting Periodl
  - The proportion of patients aged 65 years, receiving tofacitinib, who have ≥1 prescription dispensing of tofacitinib from the time they turn 65.5 years old through to the end of the follow-up period and a history of alternative treatments *prior to* that tofacitinib prescription dispensing, reported overall and by approved indication and stratified by VTE Reporting Periodk and CV and Malignancy Reporting Periodl

<sup>1 Hungary will not have a CV and Malignancy Reporting Period 1 or a CV and Malignancy Reporting Period 2 for PsA and UC.

- Use in patients with CV risk factors, as measured by:e
  - The proportion of patients with evidence of ≥1 CV risk factors *prior to* initiation of tofacitinib, reported overall and by approved indication and stratified by CV and Malignancy Reporting Period
  - The proportion of patients with evidence of ≥1 CV risk factors *prior to* initiation of tofacitinib and no prior use of an alternative therapy (i.e., biologic), reported overall and by approved indication and stratified by CV and Malignancy Reporting Period
  - The proportion of patients who discontinue tofacitinib after developing ≥1 CV risk factor while taking tofacitinib, reported overall and by approved indication and stratified by CV and Malignancy Reporting Period
  - The proportion of patients who continue taking tofacitinib after developing ≥1 CV risk factor while taking tofacitinib, reported overall and by approved indication and stratified by CV and Malignancy Reporting Period
- Use in patients with malignancy risk factors, as measured by:e
  - The proportion of patients with evidence of ≥1 malignancy risk factors prior to initiation of tofacitinib, reported overall and by approved indication and stratified by CV and Malignancy Reporting Period
  - The proportion of patients with evidence of ≥1 malignancy risk factors prior to initiation of tofacitinib and no prior use of an alternative therapy (i.e., biologic), reported overall and by approved indication and stratified by CV and Malignancy Reporting Period
  - The proportion of patients who discontinue tofacitinib after developing ≥1 malignancy risk factor while taking tofacitinib, reported overall and by approved indication and stratified by CV and Malignancy Reporting Period
  - The proportion of patients who continue taking tofacitinib after developing ≥1 malignancy risk factor while taking tofacitinib, reported overall and by approved indication and stratified by CV and Malignancy Reporting Period

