Average daily dose (ADD) t	Outcome: Compliance to recommended posology	Defined in Section 9.3.4. Assessed during the follow-up period.	
A patient with an ADD of >11 mg during any of the 8-week follow-up intervals and no evidence of a diagnosis for UC t	Outcome: Compliance to recommended posology	Defined as 0 ICD-10 diagnosis codes for UC prior to and including the date of the first tofacitinib prescription dispensing in an 8-week follow-up interval that has an ADD of >11 mg (ADD defined in Section 9.3.4).	

1 able 5. Operational definitions of study variables in the selected databas	Table 3.	Operational definitions of stud	y variables in	the selected	database
--	----------	--	----------------	--------------	----------

<sup>s In GKV claims, outpatient diagnoses are reported quarterly.

<sup>t The study outcomes that contain an ADD component will *not* be assessed in Hungary or the Netherlands. The Hungarian administrative claims database is unable to estimate ADD, either directly or by proxy, due to how tofacitinib is captured in the database. In the high-budget impact medication dataset of the PHARMO Database Network, neither ADD nor the number of pills per prescription is captured.

Variable	Role	Operational definition	
A patient with an ADD of $\geq$ 15 mg in Weeks 16-23, Weeks 24-31, Weeks 32- 39, and/or Weeks 40-47 of follow-up with evidence of a diagnosis for UC but no use of an alternative therapy (i.e., biologic) prior to tofacitinib initiation t	Outcome: Compliance to recommended posology	Defined as ≥1 ICD-10 diagnosis codes for UC and ≥1 prescription dispensing for a biologic (as identified by ATC codes) prior to and including the date of the index tofacitinib prescription with an ADD ≥15 mg in Weeks 16-23, Weeks 24-31, Weeks 32-39, and/or Weeks 40- 47 of follow-up (ADD defined in Section 9.3.4). Complete list of biologics in ANNEX 6. LIST OF ATC CODES FOR MEDICATIONS OF INTEREST TO AVOID WHILE TAKING TOFACITINIB. Note: This definition will miss those who have 1 10-mg BID prescription and the remaining prescriptions are 5-mg BID.	
Compliance to patient screening and laboratory monitoring prior to and during tofacitinib treatment u			

 Table 3.
 Operational definitions of study variables in the selected databases

The following recommended screenings and monitoring will be assessed in the following timeframes:

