History of malignancy (non-metastatic and metastatic; excluding non- melanoma skin cancer)	Outcome: VTE risk factor	Defined as ≥1 ICD-10 diagnosis code for malignancy (excluding non-melanoma skin cancer) in the 12 months prior to or on the day of the index tofacitinib dispensing.
Age >50 years at tofacitinib initiation	Outcome: VTE risk factor	Defined as age at tofacitinib initiation >50 years.
History of diabetes	Outcome: VTE risk factor	Defined as $\geq 1$ ICD-10 diagnosis code for diabetes in the 12 months prior to or on the day of the index tofacitinib dispensing.
History of hypertension	Outcome: VTE risk factor	Defined as ≥1 ICD-10 diagnosis code for hypertension in the 12 months prior to or on the day of the index tofacitinib dispensing.
Initiating tofacitinib with ≥1 VTE risk factor	Outcome: VTE risk factor	Defined as ≥1 VTE risk factor (as listed and defined above) identified in the 12 months prior to or on the day of the index tofacitinib dispensing (unless otherwise specified).
Number of VTE risk factors identified prior to tofacitinib initiation	Outcome: VTE risk factor	Calculated as the sum of the number of VTE risk factors (as listed and defined above) identified in the 12 months prior to or on the day of the index tofacitinib dispensing (unless otherwise specified).

Table 3.	Operational	definitions of	f study	variables in	the selected	databases
----------	-------------	----------------	---------	--------------	--------------	-----------

Variable	Role	Operational definition
Number of UC patients with: ≥1 VTE risk factor; no prior alternative therapy (i.e., biologic); and an ADD >10 mg in Weeks 16-23, Weeks 24- 31, Weeks 32-39, and Weeks 40-47 of follow-up t	Outcome: VTE risk factor	Defined as a patient meeting all of the following criteria: ≥1 ICD-10 diagnosis code for UC; ≥1 VTE risk factor (as listed and defined above); 0 prescription medication dispensings for a biologic (as identified by ATC codes) in the 12 months prior to and including the date of the index tofacitinib prescription dispensing; and an ADD of >10 mg in Weeks 16-23, Weeks 24-31, Weeks 32- 39, and Weeks 40-47 of follow-up, respectively (ADD defined in Section 9.3.4). Complete list of biologics in ANNEX 6. LIST OF ATC CODES FOR MEDICATIONS OF INTEREST TO AVOID WHILE TAKING TOFACITINIB.

 Table 3.
 Operational definitions of study variables in the selected databases

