<sup>hh Hungary will not have a VTE Reporting Period 1. Hungary will also not have a VTE Reporting Period 2 for PsA and UC.

Variable	Role	Operational definition
Number of UC patients with: $\geq 1$ VTE risk factor; no prior alternative therapy (i.e., biologic); and an ADD >10 mg in Weeks 16-23, Weeks 24- 31, Weeks 32-39, and Weeks 40-47 of follow-up t	Outcome: Changes in the utilisation of tofacitinib —VTE risk factors	
Discontinuation of tofacitinib after developing ≥1 VTE risk factors while taking tofacitinib	Outcome: Changes in the utilisation of tofacitinib —VTE risk factors	
Continuation of tofacitinib after developing ≥1 VTE risk factors while taking tofacitinib	Outcome: Changes in the utilisation of tofacitinib —VTE risk factors	
Use in the elderly (patients 2, and 3, hh and CV and Ma	65 years and older) (will be assessed lignancy Reporting Periods 1, 2, and	l separately in VTE Reporting Periods 1, l 3 ii )
Initiating tofacitinib with no prior use of an alternative therapy (i.e., biologic) among patients 65 years of age and older	Outcome: Changes in prescribing patterns—Age 65 years and older	See 'Primary Objective 2: Prescribers' adherence to the tofacitinib aRMMs – Compliance to recommendations to limitations for use in patients aged 65 years and older' for operational
Discontinuation of tofacitinib for patients who turn 65 years old while receiving tofacitinib	Outcome: Changes in prescribing patterns—Age 65 years and older	definitions.
Failure to discontinue tofacitinib for patients who turn 65 years old while receiving tofacitinib	Outcome: Changes in prescribing patterns—Age 65 years and older	
Appropriate continuation of tofacitinib for patients who turn 65 years old while receiving tofacitinib	Outcome: Changes in prescribing patterns—Age 65 years and older	

 Table 3.
 Operational definitions of study variables in the selected databases

<sup>ii Hungary will not have a CV and Malignancy Reporting Period 1 or a CV and Malignancy Reporting Period 2 for PsA and UC.

Variable	Role	Operational definition
In patients with CV risk fa 1, 2, and 3 ii and stratified b	ctors (will be assessed separately in by sex as outlined in Section 9.7.1.3.3	CV and Malignancy Reporting Periods [Use in patients with CV risk factors])

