### 9.7.1.2.2.1. Compliance to recommendations for limitations of use

### 9.7.1.2.2.1.1. Patients with VTE risk factors

The proportion of patients with one or more risk factors for VTE, identified prior to tofacitinib initiation, will be described and tabulated overall and by individual VTE risk factor (e.g., prior VTE, recent MI). Proportions will be stratified by "RA or PsA" and "UC."

The total number of VTE risk factors identified prior to tofacitinib initiation will also be described continuously and stratified by "RA or PsA" and "UC."

The proportion of patients diagnosed with UC, one or more VTE risk factors identified prior to tofacitinib initiation, and no use of an alternative therapy (i.e., biologic) prior to tofacitinib

<sup>oo The study outcomes that contain an ADD component will *not* be assessed in Hungary or the Netherlands. The Hungarian administrative claims database is unable to estimate ADD, either directly or by proxy, due to how tofacitinib is captured in the database. In the high-budget impact medication dataset of the PHARMO Database Network (Netherlands), neither ADD nor the number of pills per prescription is captured.

<sup>pp In GKV claims, outpatient diagnoses are reported quarterly.

<sup>qq Hungary will not have a VTE Reporting Period 1. Hungary will also not have a VTE Reporting Period 2 for PsA and UC.

<sup>IT This outcome (and all sub-outcomes) will not be assessed in Sweden because the Swedish national health registers do not capture the laboratory tests of interest. In GKV claims, it may not be possible to differentiate an ALC laboratory test from an ANC laboratory test, or an ALT laboratory test from an AST laboratory test. In the PHARMO Database Network, TB screening and viral hepatitis B and C testing are not captured.

initiation whose ADD in Week 16 through Week 23, Week 24 through Week 31, Week 32 through Week 39, and Week 40 through Week 47 was >10 mg will be described and tabulated.

The proportion of patients who discontinue tofacitinib after developing one or more VTE risk factors while taking tofacitinib will be described and tabulated overall and by individual VTE risk factor (e.g., VTE, MI). Proportions will be stratified by "RA or PsA" and "UC."

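### The ADD >10 mg outcome for UC patients with a VTE risk factor sits exactly on the compliant maintenance dose and cannot, by itself, separate sustained 10 mg BID use from a few days of late induction; the ≥15 mg cut-off used elsewhere in the plan should be reported beside it.

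*Protocol*

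**What the plan says.** Section 7 gives the label history. UC induction was 10 mg BID for up to 16 weeks and maintenance 5 mg BID. After the 2019 referral, 10 mg BID maintenance is not recommended for UC patients with known VTE risk factors unless there is no suitable alternative. The restricted dose is therefore 20 mg/day.

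The outcome for that restriction, in the primary list of Section 9.3.1, requires UC, at least one VTE risk factor, no prior biologic, and "an ADD >10 mg in Weeks 16-23, Weeks 24-31, Weeks 32-39; and Weeks 40-47 of follow-up". It recurs in the secondary list ("Weeks 40-47 of follow-up, stratified by VTE Reporting Period"), in both the primary and secondary parts of Table 3 ("no prior alternative therapy (i.e., biologic); and an ADD >10 mg in Weeks 16-23"), in Section 9.7.1.2.2.1.1 ("Week 40 through Week 47 was >10 mg will be described and tabulated") and in Section 9.7.1.3.1. The cut-off is >10 mg each time.

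The other two dose outcomes in Section 9.3.1 use higher cut-offs. For UC with no prior biologic it is "The proportion of patients with an ADD of ≥15 mg in Weeks 16-23, Weeks 24-31, Weeks 32-39, and/or Weeks 40-47". For patients without UC it is "an ADD of >11 mg during any of the 8-week follow-up intervals and no evidence of a diagnosis for UC".

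Section 9.9 expects most patients from Week 17 to be at 10 mg ADD. It also says, of Sweden, that the interval ADD will be imprecise and may become more so over follow-up. Section 9.3.4 leaves the database-specific ADD rule to the SAP. ADD outcomes are not assessed in Hungary or the Netherlands.

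**The concern.** A flag meant to find 20 mg/day maintenance is set at the value expected from a patient taking 10 mg/day as recommended. Any excess in the interval, however brief, crosses it. The first interval assessed starts the day after the longest labelled induction ends, so a patient who takes exactly 112 induction days but finishes them slightly late, for example after a delayed refill, can be counted with patients kept on 10 mg BID.

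The two UC dose outcomes also disagree. As worded in Section 9.3.1, patients eligible for the VTE-risk outcome are a subset of those eligible for the UC posology outcome. (Table 3 words the biologic criterion of the posology outcome differently; that is a separate matter.) A patient with an ADD of 12 mg is flagged by the first and not by the second. Within one interval, the flagged count in the subset could exceed that in the wider group, with nothing in the plan to explain it.

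At stake is how a primary outcome for the 2019 dose restriction is read. The same outcome is also tabulated by VTE Reporting Period.

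**Working it through.** Inputs:
- Compliant maintenance: 5 mg BID = 2 × 5 = 10 mg/day (Sections 7 and 9.9).
- Restricted maintenance: 10 mg BID = 2 × 10 = 20 mg/day (Section 7).
- Longest labelled induction: 16 weeks = 16 × 7 = 112 days (Section 7).
- Weeks 16-23: Day 113 to Day 168 (Section 9.3.4), so 168 − 113 + 1 = 56 days, starting the day after Day 112.

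The plan's own figures reproduce: 5 mg BID gives 10 mg ADD and 10 mg BID gives 20 mg ADD.

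If a patient spends k days of a 56-day interval at 20 mg and the remaining days at 10 mg, then ADD = (20k + 10(56 − k))/56.

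| k (days at 20 mg) | ADD (mg) | >10 | >11 | ≥15 |
|---|---|---|---|---|
| 0 | 560/56 = 10.00 | no | no | no |
| 1 | 570/56 = 10.18 | yes | no | no |
| 5 | 610/56 = 10.89 | yes | no | no |
| 6 | 620/56 = 11.07 | yes | yes | no |
| 27 | 830/56 = 14.82 | yes | yes | no |
| 28 | 840/56 = 15.00 | yes | yes | yes |

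The shortest exposure that triggers the flag is therefore 1 day for >10 mg, 6 days for >11 mg and 28 days for ≥15 mg. Carry-over of 1 to 27 days is flagged at >10 mg and not at ≥15 mg.

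The denominator matters. With one day at 20 mg, one day without supply and 54 days at 10 mg, a fixed 56-day denominator gives (20 + 0 + 540)/56 = 10.0 mg, not flagged. A covered-day denominator gives 560/55 = 10.18 mg, flagged. The protocol does not fix which applies.

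The ADD categories in Section 9.3.4 do not settle the matter. The >10 mg cut-off falls inside the category from above 5 to 11 mg, and an ADD of exactly 15 mg falls in the category from above 11 to 15 mg. Neither outcome cut-off is a category boundary.

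**The case against.** The strongest defence is that >10 mg is the label ceiling. Section 7 gives 5 mg BID as the UC maintenance dose not to be exceeded, calls the VTE risk dose-dependent, and wants 10 mg BID maintenance kept as short as possible. A stricter cut-off in the high-risk subgroup than for general UC posology is coherent. The >11 mg cut-off likewise follows from the 11 mg RA tablet. This stands: >10 mg is not wrong in itself. But the plan does not state this intent.

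Nor is ≥15 mg clearly better as the sole measure. The Table 3 note concedes "This definition will miss those who have 1 10-mg BID prescription" with the rest at 5 mg BID. On a 56-day denominator it also misses a 10 mg BID patient with 41 covered days and none otherwise: 41 × 20/56 = 14.6 mg. This too stands, and argues against replacing >10 mg.

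Third, existing reporting limits the harm. Table 3's "Weeks 40-47 of follow-up, respectively (ADD defined in Section 9.3.4" supports separate results per interval, which keeps Weeks 16-23 apart from later ones. ADD is also reported continuously and in categories by indication group, VTE risk factor, prior biologic and reporting period. This mitigates in part, but joint cross-tabulation of those factors is not stated, so the distribution for this subgroup is not assured.

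A reader might go further and infer that a large, calculable share of compliant patients will be flagged. The documents do not support that: pack sizes, refill timing, the share of patients with a full 16-week induction and the ADD rule are not given. The one example in Section 9.3.4 (Sweden) takes daily dose from DDDs or unit strength; under a strength-based rule a steady 5 mg BID patient sits at exactly 10 mg and is not flagged. A reader might also infer that the before/after picture is attenuated. That is not shown: the cut-off is the same in every VTE Reporting Period, and Section 9.7.1 plans no comparative analyses.

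**Conclusion.** The point holds as a minor one. The VTE-risk dose outcome has zero margin above the compliant ADD, against 5 mg for the parallel UC outcome in the same intervals, and the difference is unexplained. Reported alone, >10 mg cannot distinguish sustained 10 mg BID maintenance from one or a few induction days after Day 112.

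The 1-day and 28-day figures assume every other day in the interval is covered at 10 mg. Under a strength-based or days'-supply rule, the problem lies mainly in Weeks 16-23, in patients who had a full 16-week induction, and only in Sweden and Germany. How many patients that is cannot be stated from the protocol.

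**What to change.** In Section 9.3.1 (primary and secondary lists), Table 3, and Sections 9.7.1.2.2.1.1 and 9.7.1.3.1, keep ADD >10 mg as the sensitive measure and add ADD ≥15 mg beside it as the specific measure of sustained 10 mg BID maintenance. Give both for each 8-week interval, and by VTE Reporting Period in the secondary analysis. Add a sentence saying what each cut-off is for. Leave the posology outcome at ≥15 mg, and the ADD and early-refill rules to the SAP.

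The cost is protocol wording and one extra table column for Sweden and Germany; no new data are needed. With the other days at 10 mg, ≥15 mg misses fewer than 28 days at 20 mg/day in an interval, but the retained >10 mg column keeps such use visible.
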